#### **5.5.3 *Clinical Laboratory Evaluations***

Patients with clinically significant abnormal laboratory values will be identified. Clinically significant, treatment-emergent laboratory values (i.e., baseline < Grade 3 and post-baseline meets  $\geq$  Grade 3, according to CTCAE, version 5.0) will be summarized by treatment group. Laboratory values will be summarized at each time point for each treatment group, using descriptive statistics. The tables will also include changes from Baseline. Individual patient listings will be provided.

#### **5.5.4 *Physical Examination***

A listing of physical examination findings will be provided by patient. Pregnancy, alcohol screening, and drug testing results will be provided by patient.

#### **5.5.5 *Vital Signs***

Vital signs will be summarized at each time point for each treatment group, using descriptive statistics. Change from baseline in vital signs values will also be summarized. Individual patient listings will be provided.

Baseline will be defined as the last vital sign value obtained before the first dose of Study Medication on Day 1.

#### **5.5.6 *12-Lead Electrocardiogram***

The change from baseline in ECG intervals (PR, QT, QTcF, QRS, and RR) to each scheduled assessment will be summarized descriptively by treatment group. A table presenting frequencies and percentages of ECG findings described as “abnormal, clinically significant,” “abnormal, not clinically significant,” and “normal” will be provided by treatment group.

Frequency distributions of the QTcF interval will be displayed in a table by treatment group for abnormally high values that are greater than their baseline value at any post-baseline visit for the following data cuts:

- >450 msec and > Baseline value
- >470 msec and > Baseline value
- >500 msec and > Baseline value

Additionally, the change from baseline frequency distributions of the QTcF interval will be displayed in a table by treatment group for the following data cuts:

- >30 msec increase
- >60 msec increase

#### **5.5.7 *Extrapyramidal Symptoms***

Scores on the SAS, AIMS, and BARS will be summarized for each corresponding visit. Individual patient scores will be listed.

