- Standard 12-lead ECG (Weeks 6 and 12 only; if Week 6 visit is a remote visit, ECG assessment may be performed at Week 8 or 10)
- Urine pregnancy tests for women of childbearing potential
- Alcohol breath test
 - o *Patient may be discontinued if they test positive at any two visits during the treatment period*
- Serum chemistry, hematology, and coagulation parameter evaluations (Weeks 6 and 12 only)
- Serum renal parameters and urinalysis
- Blood sample for assessment of CTP-692 levels (pre-dose if dose of Study Medication is administered in the clinic at Weeks 2, 4, 6, 8, and 10)
 - o *If possible, time of last dose taken should also be recorded*
- Dispensation of Study Medication to take home
 - *A 2-week supply of the Study Medication will be provided at each visit except Week 12*
 - *When study assessments are not conducted in the clinic due to the COVID-19 pandemic, the Study Medication may be sent directly to the patient*
- PANSS (Weeks 2, 4, 8, 10, and 12)
- CGI-S (Weeks 2, 4, 6, 8, 10, and 12)
- C-SSRS (Since Last Visit version)
- PSP (Weeks 6 and Week 12 only)
- SQLS (Week 12 only)
- SAS, AIMS and BARS (Weeks 6 and Week 12 only)
- Blood sample for assessment of CTP-692 levels (post-dose; Week 12 only)
 - *Blood sample should be taken at the end of the visit*
 - *Time of CTP-692 dose and blood draw should be recorded*
- Administration of dose of Study Medication in the clinic with food *at the Week 12 visit*
 - Post Dose blood sample for assessment of CTP-692 levels (Week 12 only)
 - o *Blood sample should be taken at the end of the visit*
 - o *Time of CTP-692 dose and blood draw should be recorded*

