9. SELECTION AND WITHDRAWAL OF PATIENTS

9.1. Inclusion Criteria

1. Patient should be able to read, understand and voluntarily sign an informed consent document prior to any study related assessments and procedures being conducted. Patients should be willing to comply with the study visits and requirements of the study protocol.
2. Patient should be between 18 and 55 years of age, inclusive, at the time of signing the informed consent document.
3. Physician confirmed DSM-V diagnosis of schizophrenia for the past 2 years based on patient's history and confirmed by psychiatric evaluation and MINI International Neuropsychiatric Interview Psychotic Disorders, version 7.0.2 (MINI, Version 7.0.2; see [APPENDIX L](#)).
4. The patient is an outpatient with no hospitalization for worsening of schizophrenia within 3 months of the first Screening Visit (Week -5).
5. Patients currently treated with one antipsychotic (AP) medication which has been unchanged (medication and dose) for at least 7 weeks prior to the first Screening Visit (Week -5), and expected to remain unchanged during the Screening and Treatment period. Allowed orally dosed APs are:
 - a. Aripiprazole
 - b. Asenapine
 - c. Brexipiprazole
 - d. Cariprazine
 - e. Lurasidone
 - f. Olanzapine
 - g. Paliperidone
 - h. Quetiapine
 - i. Risperidone

Note: If the patient is being treated with depot or long-acting antipsychotics, they should be on the treatment for at least 2 drug administration cycles prior to the first Screening Visit (Week -5).

6. Patients with confirmed blood levels of their current AP medication in samples drawn at the Qualification Visit (Week -3).
7. The patient has a reliable informant who is able to provide information regarding the patient and support study participation.

8. Patients with clinically stable schizophrenia with residual symptoms defined as PANSS total score of 70-110 per evaluation at the first Screening Visit (Week -5), the Qualification Visit (Week -3) and Day 1.

Note: At Week -3 and Day 1, the PANSS total score may vary by 10 points as compared to a previous visit, as long as total score remains between 70-110 at each of the three visits for the patient to be included in the study.

Patients must also meet these additional PANSS criteria:

- a. PANSS score of ≤ 4 on positive scale items of conceptual disorganization and hostility
- b. PANSS score ≥ 4 on **at least two** of the following items:
 - a. Delusions
 - b. Hallucinations
 - c. Suspiciousness/Persecution

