18. APPENDICES

APPENDIX A: CONCOMITANT MEDICATIONS

ALLOWED MEDICATIONS	PROHIBITED MEDICATIONS
Antipsychotics Aripiprazole Asenapine Brexpiprazole Cariprazine Lurasidone Olanzapine Paliperidone Quetiapine Risperidone Contraceptives (oral and implants) Non-antipsychotic sleep medications	ADD prescription medications ADHD prescription medications Clozapine Lithium

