### **4.9 Concomitant Medications**

Concomitant medications will be reviewed and documented each visit during the study and are defined as any medications received at or after the first dose of study medication, medication that was received before initial dosing and continued after initial dosing of study medication, or medication with missing stop date.

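### SAP 5.5.7 plans only raw SAS, AIMS and BARS scores per visit, so within-patient worsening and new anti-EPS drug use are not shown by arm, although Day 1 scores are collected

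*SAP*

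**What the plan says.** SAP 5.5.7 gives the whole analysis in two sentences: "Scores on the SAS, AIMS, and BARS will be summarized for each corresponding visit", and "Individual patient scores will be listed". It plans no change from baseline, shift table or count of worsened patients. SAP 5.1.3 defines baseline and the descriptive statistics but sets no default change score.

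The neighbouring safety sections go further. For laboratory values (SAP 5.5.3), "The tables will also include changes from Baseline". For vital signs (SAP 5.5.5), "Change from baseline in vital signs values will also be summarized". SAP 5.5.6 does the same for ECG intervals.

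The data for a change score exist. Protocol 8.2.2 has the three scales rated on Day 1 before dosing and again at Weeks 6 and 12.

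On background treatment, Protocol 9.1 admits "Patients currently treated with one antipsychotic (AP) medication which has been unchanged (medication and dose) for at least 7 weeks" before the first Screening Visit, and the drug is expected to stay unchanged. Drugs given for extrapyramidal symptoms (EPS) are not mentioned. The prohibited column of Protocol Appendix A reads "ADD prescription medications ADHD prescription medications Clozapine Lithium", and the allowed column does not list them either. Protocol 10.4 leaves other medication to the investigator. SAP 4.9 counts as concomitant both drugs first received at or after the first dose and "medication that was received before initial dosing and continued after initial dosing of study medication". SAP 5.5.10 tabulates them together by drug class and preferred term, with a separate table for antipsychotics only.

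**The concern.** EPS is a named safety measure in a trial of an add-on to antipsychotics. The documents do not say that each permitted drug causes EPS. The choice of scales implies that background symptoms are expected, and SAP 4.6.2 describes the AIMS as a scale for patients on neuroleptics. The safety question for a patient is therefore whether symptoms worsen from the Day 1 level.

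A mean score at Week 12 carries between-patient differences that were present before dosing, and it may cover a different set of patients from the Day 1 mean. A patient who worsened and was then treated may score normally at Week 6 or Week 12. At stake is how clearly a modest EPS signal would appear in the by-arm tables.

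**Working it through.** **Inputs.** From SAP 5.1.1: 75 randomised and about 60 completing per arm, and for PANSS a difference of 5.2, SD 10 and two-sided 0.05. The documents give no SD or within-patient correlation for SAS, AIMS or BARS. The correlation r between Day 1 and a later visit is therefore an assumption, shown from 0.3 to 0.9, with the same SD assumed at both times. Results are in SD units.

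**The plan's own figure.** With 60 per arm, difference 5.2 and SD 10, power is 0.813 by the normal approximation and 0.806 by the t-test. This agrees with the stated figure of at least 80%, and 60/(1 − 0.20) = 75. The calculation concerns PANSS; no figure is stated for EPS.

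**Precision.** Var(change) = 2(1 − r) × Var(raw), so the SE ratio of change to raw is sqrt(2(1 − r)). For a baseline-adjusted score it is sqrt(1 − r²). With 60 per arm, the 95% half-width for active minus placebo on raw scores is 1.96 × sqrt(2/60) = 0.358 SD.

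| r (assumed) | SE ratio, change | Half-width, change (SD) | SE ratio, baseline-adjusted |
|---|---|---|---|
| 0.3 | 1.18 | 0.423 | 0.95 |
| 0.5 | 1.00 | 0.358 | 0.87 |
| 0.6 | 0.89 | 0.320 | 0.80 |
| 0.7 | 0.77 | 0.277 | 0.71 |
| 0.8 | 0.63 | 0.226 | 0.60 |
| 0.9 | 0.45 | 0.160 | 0.44 |

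Change is more precise than the raw score only if r exceeds 0.5.

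**Different patients at different visits.** Non-completers are 75 − 60 = 15, and 15/75 = 20%. That is the largest share of the Day 1 mean that could be absent at Week 12, and it is reached only if no Early Termination (ET) scores are obtained or used. If those patients' Day 1 mean were k SD above that of completers, the all-patient Day 1 mean would exceed the completers' by 0.20 × k: 0.05 SD at k = 0.25, 0.10 at 0.5 and 0.20 at 1.0. The difference of two visit means would then not equal the mean within-patient change.

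The placement of ET scores is unclear. SAP 5.1.5 speaks of data in general, but Table 2, which holds the windows, is titled for efficacy assessments. If it were applied to EPS, an ET score on Days 22 to 35 would fall in Week 4, where no EPS rating is scheduled.

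**Attenuation by treatment (illustration).** Suppose a share w of an active arm worsens by 2 SD and a fraction m of those patients is treated back to baseline. The mean shift is 2w(1 − m). At w = 10% it is 0.20 SD with m = 0, 0.10 with m = 0.5 and 0 with m = 1. Even the untreated shift lies inside the raw half-width of 0.358 SD. Change scores do not undo this attenuation; a count of new or increased anti-EPS drugs would show it.

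**Which score.** The SAS text (Protocol 11.7.1, SAP 4.6.1) rates ten items from 1 to 5, a total of 10 to 50. Protocol Appendix G rates ten items from 0 to 4, a total of 0 to 40. The item lists also differ: the text has head rotation and akathisia, while the appendix has leg pendulousness and head dropping. No summary score is defined for the AIMS or BARS (SAP 4.6.2, 4.6.3).

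**The case against.** The strongest reply is that the trial is randomised and placebo-controlled, with summaries by arm. Placebo supplies the background EPS at each visit, and Day 1 means will stand beside the later ones. This stands in full. A reader might infer that raw scores bias the comparison or cannot show an effect against background. The documents do not support that: background EPS is balanced in expectation and mainly costs precision.

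A reader might also infer that Week 12 describes completers only. Protocol 9.3.1 and SAP 3.6 ask for all Week 12 assessments at early termination, and these include the three scales. So 20% is an upper bound, and what remains is the unclear placement of ET scores.

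It would likewise go too far to say that a worsened and treated patient is invisible. Under Protocol 12.1 worsening of a pre-existing condition is an adverse event. SAP 5.5.1 tabulates such events by arm, and Protocol 12.3.2 records treatment given for them. Anti-EPS drugs also enter the SAP 5.5.10 table. This answers the point only in part. SAP 5.5 routes clinically significant physical-examination and laboratory findings into adverse events but names no such route for scale scores. Pooling ongoing with new drugs dilutes a difference between arms, though it does not hide it.

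The standard error is not a planned statistic, since safety is descriptive only. Patient scores are listed, and SAP section 7 lets tables be changed without a SAP update. The information is therefore recoverable, but a listing of about 300 patients is not a by-arm summary.

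**Conclusion.** The point holds as a modest reporting gap. It does not threaten the validity of the comparison with placebo. SAP 5.5.7 leaves EPS without the change from baseline that laboratory values, vital signs and ECG receive, and so shows no within-patient worsening by arm. That part rests on the text alone.

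The size of any precision loss depends on an unstated correlation: change would be better at r = 0.6 to 0.8, equal at 0.5 and worse below that. A general claim that change scores are more precise is therefore not supported. The case for a paired summary does not depend on r, because it shows who worsened and compares the same patients at both times. The attenuation figures are illustrations under assumed shares; the documents give no expected rate of anti-EPS drug use.

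**What to change.** In SAP 5.5.7:

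1. State the score analysed for each of the SAS, AIMS and BARS, and reconcile the SAS item range and item list between the text and Protocol Appendix G. Change cannot be computed unambiguously until this is settled.
2. Next to the raw scores, summarise by arm the change from Day 1 at Week 6 and at Week 12/ET in patients with both values, and the number who worsened from baseline. Say where ET scores are placed.
3. Tabulate by arm the number of patients who started or increased an anti-EPS drug after Day 1, separately from drugs ongoing at Day 1.

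The cost is SAP wording and one or two extra descriptive tables from data already collected. No visit, assessment or treatment rule changes.

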#### **5.5.8 *Antipsychotic Medication Blood Level***

The presence (Yes/No) of antipsychotic medications in the blood at the Qualification Visit will be provided per patient as a listing.

#### **5.5.9 *CTP-692 Blood Level***

A listing indicating the time of CTP-692 blood draw relative to time of dose will be provided per patient.

#### **5.5.10 *Concomitant Medications***

Concomitant medications will be summarized (n and %) by ATC class and preferred term (coded by WHO Drug coding dictionary version B3 September 2020) for each treatment group. This table will also include an overall total column. Concomitant medications for individual patients will be provided in a listing. A separate table for concomitant antipsychotic medications will also be provided.

### **5.6 Study Medication Exposure**

The number of days of Study Medication administration will be summarized for each treatment group, as well as provided in a listing per patient.

### **5.7 Interim Analyses**

No interim analyses are planned for this study.

## **7 TABLES, LISTINGS AND FIGURES**

A separate document containing the list of tables, listings, and figures (TFLs) to be included in the post-text Appendix 14 of the CSR will be provided. TFLs may be modified with Sponsor's approval and as deemed necessary without update to the SAP.
